4.9.3.3 Missed work/school day in the past 4 weeks by visit

This endpoint will be analyzed using an analysis of variance (ANOVA), with treatment group and baseline IGA severity (3, 4) as covariates in the model. A 95% CI for the difference between each nemolizumab dose regimen and placebo in LSMeans and p-value will be calculated based on contrast test statistics.

Total number of missing days during the treatment period will be summarized by treatment group.

4.9.3.4 Change from baseline in EQ5D at week 24

The following endpoints will be analyzed using ANCOVA, with treatment group, baseline IGA severity (3, 4) and baseline values of the corresponding response variable as covariates in the model. A 95% CI for the difference between each nemolizumab dose regimen and placebo in LSMeans and p-value will be calculated based on contrast test statistics.

- Change from baseline in EQ5D index at week 24
- Change from baseline in EQ5D VAS at week 24
- Change from baseline in each dimension score of EQ5D at week 24

In addition, number and percentage of subjects in each level of each dimension of EQ5D will be summarized at week 24. The difference between each nemolizumab dose regimen and placebo will be tested using CMH tests based on ridit scores stratified by baseline IGA severity (3, 4).

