7.5.3 Sick leave/missed school day

Subjects who are employed or enrolled in school/university at baseline will be asked to report the number of missed work/school days due to AD since the last visit (or since the last 4 weeks at Week 4) not including missed work/school days due to participation in this clinical trial.

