8.1.2.4 Visit 5 – 9 /Week 4-20

During the visits at week 4 – 20, the following procedures/assessments will be conducted at each visit:

1. Ask the subject to complete the DLQI and HADS questionnaires (both questionnaires **at week 12 visit only**). Ask the subject about the missed work/school days since the last 4 weeks.
2. Collect information regarding AE (including review of laboratory values) and concomitant therapies/procedures.
3. Check subject's record for pruritus NRS, PCS and sleep disturbance NRS, and remind subject to complete them daily.
4. Complete the evaluation of EASI, IGA, and SCORAD (including BSA).
5. Perform a physical examination (including weight and the evaluation of prurigo nodularis lesions if applicable), vital signs measurements and ECG (**ECG at week 12 only**).
6. Conduct respiratory medical assessments, including PEF for subjects with a history of asthma.
7. Complete UPT if the subject is a female of childbearing potential.
8. Collect urine for urinalysis.
9. Collect blood sample for hematology, blood biochemistry, PK, and TARC analysis. Collect blood sample for biomarker analysis (including IgE) and ADA (**at weeks 4, 8 & 16 only**).
10. Collect stratum corneum samples for biomarker analysis (**at week 16 visit only**).
11. **Partially unblinded pharmacist will:**
 - 11.1. Prepare the syringe containing 1.0mL of dosing solution of appropriate concentration of nemolizumab or placebo according to the pharmacy manual and the specific instruction provided by the IRT system;
 - 11.2. Provide the prefilled syringe to the blinded investigator or qualified personnel for injection.
12. Blinded investigator or qualified personnel will administer the study drug subcutaneously to the subject, and observe carefully before discharging the subject (**for at least 30 minutes at week 4 only**).

13. Collect the returned TCS. Dispense TCS and, if needed, moisturizer, and provide instruction on their usage. Instruct subject to bring used and unused TCS back to investigational site at each visit.
14. Schedule the following visit.

8.1.2.5 *Visit 10/End of Treatment/Week 24*

During the end of treatment visit at week 24, the following procedures/assessments will be conducted:

1. Ask the subject to complete the DLQI, HADS and EQ5D questionnaires. Ask the subject about the missed work/school days since the last visit.
2. Collect information regarding AE (including review of laboratory values) and concomitant therapies/procedures.

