3.2.6.3 Sick leave/missed school day

Subjects who are employed or enrolled in school/university at baseline will be asked to report the number of missed work/school days due to AD since the last visit (or since the last 4 weeks at week 4) not including missed work/school days due to participation in this clinical trial.

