4.6 Treatment Compliance

Subject compliance with study treatment will be assessed via relative dose (%) of study drug. Refer to Section 4.8.1 for more analyses.

Study drug usage: Actual Dose (mg) of study drug at each planned dosing day is defined as

CCI

where: start volume in syringe = 1.0 mL.

Actual Total Dose (mg) is defined as the sum of the actual doses (mg) administered to a subject during a specified period.

Prescribed Total Dose (mg) is defined as the sum of the prescribed doses (mg) to a subject during a specified period.

Relative Dose (%) is defined as

CCI

The study drug compliance will be evaluated according to number of injections. Subjects with a compliance rate (number of actual injection / number of planned injection x 100) between 80% and 120% is considered as compliant with study drug during their participation in the study. Proportion of subjects considered as compliant with study drug will be summarized.

TCS usage: TCS are dispensed at screening, baseline, weeks 4, 8, 12, 16, 20, 24, 28, and returned at subsequent visit and weighted. Additional dispensation and weight may also occur at weeks 1 & 2, and/or unscheduled visits.

Actual Dose (g) at each planned dosing interval (one dispensation-return cycle) is defined as

CCI

In general, this will be considered as the monthly TCS usage. TCS dispensed at baseline, week 1 and 2 (returned at weeks 1, 2 and 4, respectively) will be summed up to get the TCS usage for the first month.

Actual Total Dose (g) of background TCS is defined as the sum of the actual doses (g) administered to a subject during a specific period (e.g., during the study treatment period). This information during the follow-up period should also be included. TCS usage will be presented by potency level and overall.

CCI

For missing TCS, the following rules will be followed:

- Dispensed weight: missing; returned weight: not missing
Impute the missing dispensed weight by the weight of another intact tube (entered by site).

- Dispensed weight: missing; returned weight: missing
The worst case scenario is that the subject has used the entire tube. Therefore, consider to use the content of the entire tube (45, 50, 15 or 30g depending on the actual TCS) instead of imputing the missing data. So the result of subtracting returned weight from dispensed weight is the content of the tube i.e. return weight imputed as 0.

- Dispensed weight: not missing; returned weight: missing

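### Missed work/school days are collected over conflicting recall periods and analysed as four-week counts and totals with no denominator for the time covered

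*SAP*

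**What the plan says.** Three descriptions of the same variable do not agree.

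- **Collection, general rule.** SAP 3.2.6.3 asks employed or studying subjects for the "number of missed work/school days due to AD since the last visit", with a four-week recall at week 4 only. Protocol 7.5.3 gives the same rule.
- **Collection, visit instructions.** For weeks 4 to 20, Protocol 8.1.2.4 says: "Ask the subject about the missed work/school days since the last 4 weeks". For week 24 (Protocol 8.1.2.5) and early termination (8.1.4.1) it says: "Ask the subject about the missed work/school days since the last visit".
- **Analysis.** SAP 4.9.3.3 is titled "Missed work/school day in the past 4 weeks by visit". It fits an ANOVA with treatment group and baseline IGA and gives 95% CIs and p-values for each dose against placebo. It adds: "Total number of missing days during the treatment period will be summarized by treatment group". It has no time denominator, no offset and no rule for incomplete follow-up.

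For background TCS, SAP 4.6 measures each dispensation-return cycle and states: "In general, this will be considered as the monthly TCS usage". The cycles dispensed at baseline, week 1 and week 2 are added to make the first month, and the total is a sum of cycles. The formula for the amount used and one further block in that section are redacted.

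**The concern.** A count of days missed means something only relative to the time it covers. If that time varies between subjects, the by-visit comparison partly reflects attendance, and the treatment-period total partly reflects how long a subject stayed. The by-visit analysis carries formal p-values, so a reader will take it as a productivity result. The recall conflict adds a second problem: the same skipped visit produces a different error depending on which instruction a site followed, and the analysis dataset would not show which.

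**Working it through.** **Inputs.** Target days 1, 29, 57, 85, 113, 141 and 169, with windows of ±1 day (week 4), ±3 (week 8) and ±5 (weeks 12 to 24), from Protocol Table 2 and SAP Appendix 1. Treatment period 24 weeks. The documents give no rates for dropout or skipped visits; those below are assumptions.

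**1. The plan's own figure.** Successive target days from baseline to week 24 differ by 28 (for example 113 − 85 = 28). The four-week label is therefore right when every visit is attended on its target day.

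**2. Visits attended within window.** From week 12 onward the interval is 28 ± (5 + 5) = 18 to 38 days. Relative to 28 days that is 18/28 = 0.64 to 38/28 = 1.36.

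**3. One skipped visit, recall since the previous visit.** Week 16 to week 24 is 169 − 113 = 56 days, and 56/28 = 2.0. Within windows it is 46 to 66 days, or 1.64 to 2.36. If a share *s* of the subjects contributing at a visit skipped the one before, the mean at that visit is (1 − *s*) × 1 + *s* × 2 = 1 + *s* times the true 28-day mean: 5% too high for *s* = 5%, 10% too high for *s* = 10%. The treatment-period total loses nothing.

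**4. One skipped visit, four-week recall.** The by-visit value is right, but the total loses 4/24 = 17% at a constant rate.

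**5. Which case applies.** At weeks 8 to 20 it depends on whether the site follows Protocol 7.5.3 or 8.1.2.4. At week 24 the collection texts agree on recall since the previous visit, so step 3 applies after a skipped week 20.

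**6. Early termination.** SAP 4.2 slots early termination assessments by day range, with week 24 covering days 156 to 183. A visit on day 156 after one on day 141 covers 15 days (15/28 = 0.54) and would count as a week 24 value. The same section also says missed days follow the actual scheduled visits, so the handling is unclear as well as unscaled.

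**7. Totals for early leavers at an equal rate.** The share of a completer's total is weeks observed / 24: week 4, 17%; week 8, 33%; week 12, 50%; week 16, 67%; week 20, 83%.

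**8. Illustration by arm, equal true rates, assumed dropout.** If a share *d* leaves evenly over 24 weeks, the mean total is 1 − *d*/2 of the full amount.

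| Placebo *d* | Active *d* | Placebo total | Active total | Active / placebo |
|---|---|---|---|---|
| 10% | 10% | 95% | 95% | 1.000 |
| 20% | 10% | 90% | 95% | 1.056 |
| 30% | 10% | 85% | 95% | 1.118 |
| 10% | 20% | 95% | 90% | 0.947 |

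The artefact vanishes with equal dropout and reverses if more active subjects leave.

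**The case against.** Four points can be made against this, and each limits it.

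- **A reader might infer that a skipped visit always doubles a month.** It does not. Protocol 8.1.2.4 asks about four weeks at weeks 4 to 20, which matches the SAP title; there a skipped visit loses time from the total and leaves the next value intact. Doubling needs the other recall wording, or week 24 after a skipped week 20.
- **A reader might extend the fault to TCS use.** The visible text points to a plain weight difference, but two blocks in SAP 4.6 are redacted and time scaling may be among them. The section also qualifies the monthly label as general. SAP 4.7.4.7 excludes rescue users from all TCS analyses, and an unreturned tube counts as fully used, which pushes an early leaver's recorded amount up. The dropout illustration therefore does not carry over to TCS.
- **A reader might conclude that a benefit of nemolizumab is hidden.** That needs more leavers on placebo, and the documents give no rates. Subjects who stop study drug are asked to stay for all visits, so only those who leave the study are affected. If placebo subjects instead skipped more visits under the since-last-visit recall, placebo by-visit values would rise, in the drug's favour.
- **Leavers shorten totals, not by-visit means.** The p-values attach to the by-visit values; the total is only summarised.

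What stands after these points is the conflict in recall, the unscaled by-visit count and the total without a denominator.

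**Conclusion.** The point holds for missed work/school days. The collection texts contradict one another, the analysis label matches only one of them, and no visible rule relates a count to the time it covers. A single value can represent 0.64 to 1.36 of a 28-day period with every visit in window, and about twice that period after a skipped visit where the recall runs from the previous visit. A leaver's total is reduced in proportion to weeks observed. These figures assume a constant rate of missed days within subject.

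Neither the direction nor the size of a between-arm bias can be stated from the documents, and nothing can be asserted about TCS beyond a conditional request. This is a minor point: missed days are a productivity measure, TCS use is a descriptive endpoint in the SAP's other-efficacy group, and the primary endpoint and sample size are untouched.

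**What to change.** - **Recall.** Use one window, since the last visit, in Protocol 7.5.3 and 8.1.2.4 and in the SAP. Define the last visit as the previous one at which missed days were recorded, with baseline as the start for week 4, and derive the days covered from visit dates already collected.
- **Total (SAP 4.9.3.3).** Report total missed days divided by total days covered, times 28.
- **By-visit analysis (SAP 4.9.3.3).** Use days covered as the denominator: a count model with a log-time offset, or a rate with a stated minimum interval. Scaling every short interval to 28 days without a minimum would create outliers; two days missed over a three-day interval before early termination would become 2 × 28/3 = 18.7. State which analysis visit, if any, an early termination value enters.
- **TCS (SAP 4.6 and 4.7.4.7).** If the redacted text does not already scale by time, report grams per 28 days observed alongside the total.

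The cost is a wording clarification in two protocol sections, SAP text, slightly more derivation work, and a change of scale for a productivity endpoint and, if the condition applies, a descriptive one. No new data are needed.

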4.10 Determination of Sample Size

Sample size is estimated using MCP-Mod approach by selecting a set of candidate dose response shapes based on EASI response in previous Phase 2a study (CIM003JG study report 2017). Refer to Section 4.7.2 on the models considered as candidates in the estimation of sample size.

Assuming a placebo response of 35%, standard deviation 45% and a maximum treatment difference of 30%, in terms of percent change from baseline in EASI, 50 subjects per arm will provide at least 90% power to detect a statistically significant dose-response for at least one model at 1-sided significance level of 0.025.

4.11 Changes in the Conduct of the Study or Planned Analysis

Changes in the conduct of the study may be instituted through a protocol amendment. Planned analyses will be revised as appropriate. Similarly, planned analyses may be changed as a result of planned blinded data reviews. Changes will be finalized prior to database lock.

The following endpoints are added:

- Secondary efficacy endpoint: Proportion of subjects achieving IGA success (defined as IGA 0 [clear] or 1 [almost clear]) and a reduction of ≥ 2 points at each visit up to week 24
- Other efficacy endpoint: Proportion of subjects achieving PCS success (defined as a weekly prorated rounded average PCS ≤ 1 [none - mild]) at each visit including follow-up visits

The following endpoint is revised:

- Secondary efficacy endpoint: Proportion of subjects with EASI-50, EASI-75 or EASI-90 (defined as achieving 50%, 75% or 90% reduction from baseline in EASI score) at each visit up to week 24 (at week 24 per the protocol)

Appendix 1 Schedule of assessments

Study Period Visit (V)	Run-in V1 ^a	V2 ^b	V3	V4	V5 ^b	Treatment V6 ^b	V7 ^b	V8 ^b	V9 ^b	V10 ^b	Follow-up V11	Follow-up V12/FINA L ^b	W32 D225	Unscheduled visit ^{b,c} (if applicable)	Early Termination Visit ^{b,d} (if applicable)
Week (W)	Screening	Baseline	W1	W2	W4	W8	W12	W16	W20	W24	W28	W32			
Day (D)	g/D -28 to -15	Baseline	D8	D15	D29	D57	D85	D113	D141	D169	D197	D225			
Visit window (±d)			± 1d	± 1d	± 1d	± 3d	± 5d	± 5d	± 5d	± 5d	± 7d				
ICF and country specific consent form (if applicable)	X														
Demographics	X														
Medical history/ Prior therapies	X														
Concomitant therapies	X	X	X	X	X	X	X	X	X	X	X	X	X	(X)	X
Inclusion/Exclusion criteria	X	X													
EFFICACY/SUBJECT-REPORTED OUTCOMES ASSESSMENTS															
DLQI	X	X		X		X	X			X					X
HADS	X	X				X	X			X					X
EQ5D	X	X				X	X			X					X
5-D itch	X	X		X		X	X			X					X
Missed work/school day				X		X	X			X					X
Pruritus NRS (daily) ^e	X	X		X		X	X			X					X
PCS (daily) ^e	X	X		X		X	X			X					X
Sleep disturbance NRS (daily) ^e	X	X		X		X	X			X					X
EASI	X	X	X	X	X	X	X	X	X	X	X	X	X	(X)	X
IGA	X	X	X	X	X	X	X	X	X	X	X	X	X	(X)	X
BSA	X	X	X	X	X	X	X	X	X	X	X	X	X	(X)	X
SCORAD	X	X	X	X	X	X	X	X	X	X	X	X	X	(X)	X
DPS ^f	X	X		X		X	X			X					X

CONFIDENTIAL

Study Period Visit (V)	Run-in V1 ^a	Treatment V5 ^b - V6 ^b	V7 ^b	V8 ^b	V9 ^b	V10 ^b	Follow-up V11 ^b - V12 ^b /FINA ^L _b	Unscheduled visit ^{b,c} (if applicable)	Early Termination Visit ^{b,e} (if applicable)	
Week (W) Day (D)	Screening g/D -28 to -15	V4 W2 D15 ± 1d	V5 W4 D29 ± 1d	V6 W8 D57 ± 3d	V7 W12 D85 ± 5d	V8 W16 D113 ± 5d	V9 W20 D141 ± 5d	V10 W24 D169 ± 5d	W28 D197 ± 7d	W32 D225 ± 7d
Visit window (±td)										
LABORATORY/SAFETY ASSESSMENTS										
AE recording (including review of laboratory values if applicable)	X	X	X	X	X	X	X	(X)	X	
Physical examination (including the evaluation of prurigo nodularis lesions if applicable)	X	X	X	X	X	X	X	(X)	X	
Height	X			X	X	X		(X)		
Weight	X			X	X	X		(X)		
ECG	X			X	X	X		(X)	X	
Vital signs	X	X	X	X	X	X	X	(X)	X	
Respiratory assessment ^g	X	X	X	X	X	X	X	(X)	X	
Urinalysis	X	X	X	X	X	X	X	(X)	X	
Hematology	X	X	X	X	X	X	X	(X)	X	
Blood chemistry	X	X	X	X	X	X	X	(X)	X	
TB test	X			X	X	X		(X)		
Hepatitis B and C test	X			X	X	X		(X)		
HIV test	X			X	X	X		(X)		
Pregnancy test ^h	X			X	X	X		(X)		
TARC	Serum	Urine	Urine	Urine	Urine	Urine	Urine	(Urine)	Urine	
Blood sample for biomarkers (including IgE)	X	X	X	X	X	X	X	(X)		
Stratum corneum sample for biomarkers	X	X	X	X	X	X	X			

CONFIDENTIAL

Study Period Visit (V)	Run-in V1 ^a	V2 ^b	V3	V4	V5 ^b	Treatment V6 ^b	V7 ^b	V8 ^b	V9 ^b	V10 ^b	Follow-up V11 ^b	Unscheduled visit ^{b,c} (if applicable)	Early Termination Visit ^{b,e} (if applicable)
Week (W)	Screening	Baseline	W1	W2	W4	W8	W12	W16	W20	W24	W28	W32	
Day (D)	g/D -28 to -15	e/D 1	D8	D15	D29	D57	D85	D113	D141	D169	D197	D225	
Visit window (±d)			± 1d	± 1d	± 1d	± 3d	± 5d	± 5d	± 5d	± 5d	± 7d	± 7d	

PK AND ADA ASSESSMENTS

PK samples
 ADA samples

STUDY DRUG AND BACKGROUND THERAPIES

Randomization
 Subcutaneous study drug injection
 TCS dispensing (D) / Return (R) and moisturizer dispensing if necessary

^a Screening visit must be performed at least 14 days prior to the day 1 visit to ensure that each subject undertakes at least 14 days of TCS treatment prior to randomization.
^b Subjects are required to fast for at least 8 hours before the visit.
^c Assessments to be conducted at the unscheduled visit depend on the reason for the visit. PK and ADA analyses are obligatory at unscheduled visits for safety reasons.
^d Subjects discontinued before the week 24 visit should attend an early termination visit and a final visit 12 weeks after the last study drug injection.
^e Pruritus NRS and PCS to be recorded by subjects once daily in the evening. Sleep disturbance NRS to be recorded by subjects once daily in the morning.
^f DPS to be recorded by subjects at 2, 4, 8, 24, 48, and 72 hours after the study drug administration on day 1.
^g PEF will be measured for subjects with a medical history of asthma only.
^h Only for females of childbearing potential. Serum pregnancy test to be performed at screening visit, and urine pregnancy test for all other visits.
ⁱ Stratum corneum sample from lesional and non-lesional skin on day 1 and from lesional skin only at week 16.

CONFIDENTIAL

Appendix 2 Criteria for potentially clinically significant vital signs and weight

Pulse rate

≤ 50 bpm and decrease from baseline ≥ 20 bpm

≥ 120 bpm and increase from baseline ≥ 20 bpm

To be applied for all positions (including missing).

SBP

≤ 95 mmHg and decrease from baseline ≥ 20 mmHg

≥ 160 mmHg and increase from baseline ≥ 20 mmHg

To be applied for all positions (including missing).

DBP

≤ 45 mmHg and decrease from baseline ≥ 10 mmHg

≥ 110 mmHg and increase from baseline ≥ 10 mmHg

To be applied for all positions (including missing).

Weight

$\geq 5\%$ increase from baseline

$\geq 5\%$ decrease from baseline

Appendix 3 Dermatology Life Quality Index (DLQI)

The DLQI questionnaire is designed for use in adults, i.e. subjects over the age of 16. It is self-explanatory and can be simply handed to the subject who is asked to fill it in without the need for detailed explanation. It is usually completed in one to two minutes.

Scoring

The scoring of each question is as follows:

Response	Score
Very much	scored 3
A lot	scored 2
A little	scored 1
Not at all	scored 0
Not relevant	scored 0
Question unanswered	scored 0
Question 7: "prevented work or studying"	scored 3

The DLQI is calculated by summing the score of each question resulting in a maximum of 30 and a minimum of 0. The higher the score, the more quality of life is impaired. The DLQI can also be expressed as a percentage of the maximum possible score of 30.

****Please Note:** That the scores associated with the different answers should not be printed on the DLQI itself, as this might cause bias**

Meaning of DLQI Scores

0-1 = no effect at all on subject's life

2-5 = small effect on subject's life

6-10 = moderate effect on subject's life

11-20 = very large effect on subject's life

21-30 = extremely large effect on subject's life

Detailed analysis of the DLQI

The DLQI can be analyzed under six headings as follows:

Section	Questions	Score
Symptoms and feelings	Questions 1 and 2	Score maximum 6
Daily activities	Questions 3 and 4	Score maximum 6
Leisure	Questions 5 and 6	Score maximum 6
Work and School	Question 7	Score maximum 3
Personal relationships	Questions 8 and 9	Score maximum 6
Treatment	Question 10	Score maximum 3

The scores for each of these sections can also be expressed as a percentage of either 6 or 3.

Interpretation of incorrectly completed questionnaires

There is a very high success rate of accurate completion of the DLQI. However, sometimes subjects do make mistakes.

- If one question is left unanswered this is scored 0 and the scores are summed and expressed as usual out of a maximum of 30.
- If two or more questions are left unanswered the questionnaire is not scored.
- If question 7 is answered 'yes' this is scored 3. If question 7 is answered 'no' but then either 'a lot' or 'a little' is ticked this is then scored 2 or 1. If "Not relevant" is ticked, the score for Question 7 is 0. If it is answered 'no', but the second half is left incomplete, the score will remain 0.
- If two or more response options are ticked, the response option with the highest score should be recorded.
- If there is a response between two tick boxes, the lower of the two score options should be recorded.
- The DLQI can be analyzed by calculating the score for each of its six sub-scales (see above). When using sub-scales, if the answer to one question in a sub-scale is missing, that sub-scale should not be scored.

Minimal Clinically Important Difference of the DLQI

For **general inflammatory skin conditions** a change in DLQI score of at least 4 points is considered clinically important (Basra et al, 2015). This means that a subject's DLQI score has to either increase or decrease by at least 4 points in order to suggest that there has actually been a

meaningful change in that subject's quality of life since the previous measurement of his/her DLQI scores.

Reference

Basra MK et al. Determining the minimal clinically important difference and responsiveness of the Dermatology Life Quality Index (DLQI): further data. *Dermatology*, 2015; 230(1):27-33.

